11.0 STUDY ASSESSMENTS

11.1 Baseline/screening evaluations

Within 28 days prior to registration:

- Informed consent and HIPAA authorization will be obtained according to ICH/GCP guidelines prior to performing any study-specific procedures.
- Medical and smoking history will be recorded.
 - Medical history must include all active conditions and any condition diagnosed within the prior 10 years that are considered to be clinically significant by the investigator. Details regarding the disease for which the participant has enrolled in this study will be recorded separately and not listed as medical history.
- Disease details and treatments will be recorded.
 - This information will include: BCLC stage at diagnosis and current BCLC stage, and all prior cancer treatments (e.g. surgery, ablation, liver-directed therapy).
- Assessment of vital signs, physical examination, assessment of ECOG status, weight, height, baseline AEs and medications.
 - Medication history will include any prior medication use within 28 days before starting on study, including indication and any protocol-related washout requirement. Treatment for the disease for which the participant has enrolled in this study will be recorded separately and not listed as a prior medication.
- Assessment of eligibility based on inclusion/exclusion criteria by treatment investigator (Section 5.0).
- Multiphasic contrast CT or MRI of abdomen/pelvis and CT chest with or without contrast for baseline disease assessment, as well as confirmation of measurable disease and at least 1 appropriate target lesion per RECIST v1.1. As clinically indicated, bone scan and contrast-imaging of neck may be obtained.
- Archival tissue will be requested if available. If archival tissue is not available, an optional fresh core biopsy may be performed (if safe and feasible).
 - For patients who had prior next-generation gene sequencing analysis of their tumor, the gene sequencing assay results will be requested.

Within 14 days prior to registration:

- CBC with differential (including hemoglobin, hematocrit, leukocyte count, neutrophils, lymphocytes, monocytes, eosinophils, basophils, and platelets).
- Serum chemistry (including sodium, bicarbonate, potassium, calcium, magnesium, phosphate, glucose, albumin, total protein, blood urea nitrogen, creatinine, alanine aminotransferase, aspartate aminotransferase, alkaline phosphatase, and total bilirubin).

- PT/INR and PTT.
- Lactate dehydrogenase (LDH)
- Pregnancy test by serum HCG (for women of child-bearing potential only).
- Alpha fetoprotein.

11.2 On study evaluations

Patients will be monitored for response to therapy (disease assessment, see Section 13.0) every 9 weeks (every 3 cycles), and for AEs continuously from the time of consent to 30 days after discontinuation of drug.

Cycles 1 Days 1, 8, 15

NOTE: Cycle 1 day 1 testing does not need to be repeated if completed within 7 days prior.

- Assessment of vital signs, physical examination, ECOG status, and weight.
- Assessment of AEs and medications. Medication start/stop dates and indication for use during the study will be recorded.
- CBC with differential (Days 1 and 15 only) (including hemoglobin, hematocrit, leukocyte count, neutrophils, lymphocytes, monocytes, eosinophils, basophils, and platelets).
- Serum chemistry (Days 1 and 15 only) (including sodium, bicarbonate, potassium, calcium, magnesium, phosphate, glucose, albumin, total protein, blood urea nitrogen, creatinine, alanine aminotransferase, aspartate aminotransferase, alkaline phosphatase, and total bilirubin).
- PT/INR, PTT (Day 1 only).

Cycles 2+ Day 1 (\pm 2 days):

- Throughout the trial, patients will complete the Cabozantinib Drug Diary (Appendix 2). This will be collected on Day 1 of each cycle.
- Assessment of vital signs, physical examination, ECOG status, and weight.
- Assessment of AEs and medications. Medication start/stop dates and indication for use during the study will be recorded.
- CBC with differential (including hemoglobin, hematocrit, leukocyte count, neutrophils, lymphocytes, monocytes, eosinophils, basophils, and platelets).
- Serum chemistry (including sodium, bicarbonate, potassium, calcium, magnesium, phosphate, glucose, albumin, total protein, blood urea nitrogen, creatinine, alanine aminotransferase, aspartate aminotransferase, alkaline phosphatase, and total bilirubin).
- PT/INR, PTT.

Every 2 cycles starting at Cycle 3 Day 1 (\pm 2 days):

- HBsAg (for patients who are HBcAb+ and HBsAg- at baseline), or HBV DNA (for patients who are HBcAb+ and HBsAg+ at baseline). If HBsAg becomes positive on study, HBV DNA should then be followed.
- TSH with reflex T4, cortisol, amylase, lipase.
- Urinary protein to creatinine ratio.
- EKG.

At the end of every 3 cycles (prior to Cycles 4, 7, 10, etc):

Multiphasic contrast CT or MRI of abdomen/pelvis, as well as CT chest with or without contrast for disease assessment as per RECIST v1.1. The same imaging technique should be used throughout the study. If there is disease progression and the patient continues treatment beyond progression, repeat imaging must be obtained 4 weeks later to confirm PD. As clinically indicated, bone scan and contrast-imaging of neck may be obtained.

Every 3 cycles starting at Cycle 4 Day 1 (± 2 days):

- Alpha fetoprotein level (if abnormal at baseline).

11.3 Assessment of safety parameters at baseline and during study treatmentLaboratory assessments

Blood samples will be collected at the time points specified and analysed in a laboratory facility at the local investigational site. In the event of AEs or lab abnormalities, additional tests and/or more frequent lab monitoring may be obtained at the discretion of the treating investigator.

Safety laboratory assessment at baseline and on treatment must include at least the following parameters. Also see Appendix 3.

At baseline and every cycle	
Complete blood count	Hemoglobin, hematocrit, leukocyte count, neutrophils, lymphocytes, monocytes, eosinophils, basophils, platelets
Serum chemistry	Sodium, bicarbonate, potassium, calcium, magnesium, phosphate, glucose, albumin, total protein, blood urea nitrogen, creatinine, alanine aminotransferase, aspartate aminotransferase, alkalinephosphatase, total bilirubin. Glomerular Filtration Rate (GFR) will be estimated by the Cockcroft-Gault formula using serum creatinine values (see Appendix 7).
Coagulation	PT/INR, PTT
Miscellaneous	LDH (baseline only)
At baseline and every 2 cycles	
Hepatitis B virus	At baseline: HBcAb and HBsAg. On study: 
 • HBsAg (for patients who are HBcAb+ and HBsAg- at baseline), or HBV DNA (for patients who are HBcAb+ and HBsAg+ at baseline). • If HBsAg becomes positive on study, HBV DNA should then be followed.
Monitoring for immune toxicity	TSH with reflex T4, cortisol, amylase, lipase
Urine protein	Urinary protein to creatinine ratio
QTc	EKG

Assessment of other safety parameters

- *Physical examination, ECOG performance score*

A physical examination will be performed at screening and at the time points specified in the Study Calendar.

A full physical exam serves as a clinical tumor assessment and should include cardiopulmonary and abdominal examinations and an assessment of the mental and neurological status. Wherever possible, the same investigator should perform this examination.

Measurement of height (in cm), body weight (in kg) and body temperature and the evaluation of the ECOG performance score will be performed at the time points specified in the Study Calendars.

- *Vital signs*

Vital signs include blood pressure and pulse after resting and sitting for at least 5 minutes, respiratory rate, oxygen saturation, and temperature. These will be recorded at the screening visit and at the time points specified in the Study Calendar.

- *Demographics and history*

Demographics (sex, birth date), information on smoking history, and pre-existing medical conditions will be collected during the screening visit.

Information on the etiology of HCC, including history of HBV, HCV, alcohol abuse, non-alcoholic steatohepatitis, or other will be collected at the screening visit. Specifically, for patients known to have HBV or HCV, details on prior anti-viral therapy, dates of therapy and response will be recorded.

The date of first diagnosis of HCC (month and year are sufficient) and tumor histology if prior pathology results are available will be reported in the CRF. Moreover, BCLC stage at initial diagnosis and current BCLC stage will be recorded, as well as the current number and locations of metastatic sites (liver, lung, lymph nodes, peritoneum, other), presence of vascular invasion (specify location). Previous treatments including surgery, catheter-based therapy, and radiotherapy will be documented, including start and end dates (month and year are sufficient) and the best response obtained (complete response, partial response, stable disease, progressive disease, unknown).

11.4 Evaluations at treatment discontinuation (at 30 days [+ 7 days] following last dose of cabozantinib or pembrolizumab)

- Collection of the Cabozantinib Drug Diary, if not previously collected.
- Assessment of vital signs, physical examination, ECOG status, and weight.
- Assessment of AEs and medications. Medication start/stop dates and indication for use during the study will be recorded.
- CBC with differential.

- Serum chemistry.
- PT/INR and PTT.
- Alpha fetoprotein.
- Most recent imaging will be used for the treatment discontinuation visit: multiphasic contrast CT or MRI of abdomen/pelvis, as well as CT chest with or without contrast. As clinically indicated, bone scan and contrast-imaging of neck may also be obtained.

11.5 Post-study follow-up

Subjects will return approximately 30 days after their last dose of cabozantinib or pembrolizumab (i.e. treatment discontinuation visit) to complete end-of-study assessments (see Section 11.4). Unused study drug will be returned by the subject. If a participant initiates a new anti-cancer therapy within 30 days after the last dose of trial treatment, the treatment discontinuation visit must occur before the first dose of the new therapy.

All treatment-related AEs will be followed until resolution, return to baseline, or deemed clinically insignificant by the treating investigator, including those that occur during the 30-day period after treatment discontinuation. Moreover, any known SAE attributed to study treatment that occurs more than 30 days after treatment discontinuation must be followed until either resolution, return to baseline, or determination by the investigator that the event has become stable or irreversible; all concomitant medications for these SAEs after 30 days from treatment discontinuation must also be recorded.

For patients who discontinue study treatment due to toxicities or reasons other than progressive disease, subsequent imaging, if available, will be requested every 4 months up to 2 years from study start date to document time of progression after coming off study. For patients who come off study due to progressive disease, patients will be followed for survival every 4 months up to 2 years from study start date (no scans will be required). Moreover, subsequent anti-neoplastic therapy receive after study discontinuation will be collected, if available.

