--	--

	
23. Has a known history of HIV infection. Note: HIV testing is not mandated for screening.
 
24. Co-infection with HBV (HBsAg (+) and /or detectable HBV DNA) and HCV (anti-HCV Ab (+) and detectable HCV RNA) at study entry.
 
25. Co-infection with HBV and HDV at study entry.
 
26. Live vaccine or live attenuated vaccine within 30 days prior to first dose of study treatment. Administration of killed vaccines is allowed.
 
27. Pregnant or lactating females.
 
28. Known psychiatric illness, substance abuse disorder, or other condition that would interfere with the ability to comply with the requirements of the study.
 
29. Has history or current evidence of any condition, therapy, or laboratory abnormality that might confound the results of the study, interfere with the subject's participation for the full duration of the study, or is not in the best interest of the subject to participate, in the opinion of the treating investigator.

Study treatments	
All enrolled patients will receive cabozantinib 40mg PO daily continuously and pembrolizumab 200mg IV every 3 weeks, in 3-week cycles. Dose modifications of cabozantinib and/or pembrolizumab may be made for adverse events (AEs) (guidelines provided in protocol). Immune-related AEs will be treated per published guidelines. If one agent needs to be discontinued due to treatment-related toxicity, patients may continue to receive treatment with the other agent.
 
Treatment will continue until disease progression, intolerance, or patient withdrawal. Treatment beyond progression will be allowed if pre-specified criteria are met (Section 12.1).

Study assessments	
Toxicity assessments (history, physical exam, labs) will occur weekly during cycle 1, then every 3 weeks on day 1 of each subsequent cycle. AEs will be graded by NCI CTCAE v5.
 
Disease assessments will be performed by multiphasic contrast CT or MRI of abdomen/pelvis, as well as CT chest with or without contrast at baseline (within one month of enrollment) and every 9 weeks on treatment. Tumor response will be determined by RECIST v1.1 and iRECIST. The tumor marker alpha-fetoprotein (AFP) will also be measured at baseline and every 9 weeks if abnormal at baseline.
 
If patients discontinue treatment due to intolerable or unacceptable toxicity, they will be followed for progression and for survival at least every 4 months up to 3 years.

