7.3 Duration of therapy

Patients will begin cabozantinib and pembrolizumab concurrently. Patients may continue study therapy until unequivocal disease progression, unacceptable drug-related toxicity, or subject withdrawal. If one drug needs to be permanently discontinued due to toxicity, the other agent may be continued. Interval dosing interruption/delay of either or both agents is allowed for AEs (see Section 9.0).

Treatment beyond progression with cabozantinib and/or pembrolizumab (depending on patient tolerance) will be allowed based on meeting pre-specified criteria and after discussion with the study PI (see Section 12.1).

Patients may be treated up to a maximum of two years from the time of treatment initiation.

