¹²EGD must be done within 6 months prior to study initiation to assess for and treat esophageal and gastric varices.

¹³Alpha fetoprotein (AFP) should be measured at baseline (within 14 days prior to registration). If abnormal at baseline, it should be measured on Day 1 of every 3 cycles starting at cycle 4, and at the treatment discontinuation visit.

¹⁴Disease assessment using multiphasic (four-phase) contrast CT or MRI of abdomen/pelvis, as well as CT chest with or without contrast should be done at baseline (within 28 days prior to registration), and every 9 weeks on treatment (every 3 cycles). If there is disease progression and the patient continues on treatment beyond progression, repeat imaging must be performed 4 weeks later to confirm progression. As clinically indicated, bone scan and contrast imaging of neck may be obtained to monitor disease (see Section 13.3). For the treatment discontinuation visit, the most recent scans are used. For patients who come off study for toxicity, subsequent restaging scans will be requested and assessed at least every 4 months for up to 2 years from study start date to document the date of progression.

¹⁵Archival tumor tissue is acceptable (paraffin-embedded tumor core biopsy or surgical specimen). If archival tissue is not available, baseline core needle biopsy may be performed (if safe and feasible).

¹⁶Pre-treatment Blood will be collected and stored for correlative studies. Research blood will be collected on Cycle 1 Day 1 and Day 8, as well as Cycle 2 Day 1.

¹⁷Informed consent/HIPAA, medical/smoking history, AE/medication assessment, physical exam/ECOG, and assessment of inclusion/exclusion criteria are completed within 28 days prior to registration. Baseline lab investigations are completed within 14 days prior to registration, including pregnancy test for women of child-bearing potential (WOCP) and AFP. Baseline imaging for disease assessment may be obtained within 28 days prior to registration.

¹⁸Cycle 1 day 1 testing need not be repeated if completed within 7 days prior.

¹⁹The treatment discontinuation visit should occur 30 days (+7 days) after the last dose of cabozantinib or pembrolizumab (whichever is latest). Most recent scans are used for the treatment discontinuation visit. Note: if a participant initiates a new anti-cancer therapy within 30 days after the last dose of trial

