treatment, the treatment discontinuation visit must occur before the first dose of the new therapy and AEs occurring until that point will be collected.

²⁰All patients who were treated will be followed for survival every 4 months with phone calls for up to 3 years from study start date. Patients who came off study for toxicity will be followed for progression with visits or by request of outside medical records every 4 months up to 3 years from study start date, where progression will be assessed by requesting and obtaining subsequent restaging scans. Subsequent anti-neoplastic therapy will be collected if available.

Abbreviations: C, cycle; q2C, every 2 cycles.

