- Discontinuation of pembrolizumab may be considered for participants who have attained a confirmed CR and have been treated for at least 8 cycles (at least 24 weeks), receiving at least 2 further cycles of cabozantinib and pembrolizumab beyond the date when the initial CR was declared.
- Completion of 2 years of therapy.
- Participant has any of the following non-overdose HECIs that are not reversible and manageable by therapy (see below). (Note: Temporary hepatic decompensation may occur in patients with cirrhosis exposed to TKIs.)
 - ALT >20 × ULN (confirmed within 1 week)
 - Drug-related total bilirubin >10 × ULN
 - CP score of > 8 points
 - Hepatic encephalopathy
 - Recurrence of a severe or life-threatening event, or of any of the laboratory abnormalities listed above, that are presumed to be immune-related
 - Uncontrolled ascites
- Subject is lost to follow-up.

Patients who come off study should be evaluated at 30 days (+ 7 days) after the last dose of cabozantinib or pembrolizumab (whichever is latest). AE assessment and reporting for patients who discontinue study treatment are described in Section 16.3.2. Furthermore, subjects who come off study for reasons other than PD will be followed for progression, and all patients who come off study will be followed for survival every 4 months for up to 2 years from study start date.

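### Survival follow-up ends at 2 years in Sections 11.5 and 12.0 but at 3 years in Table 10.1 footnote 20 and the synopsis, counted from an undefined 'study start date'

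*Combined protocol and SAP*

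**What the plan says.** **Survival.** For patients who stop because of progression, Section 11.5 says "patients will be followed for survival every 4 months up to 2 years from study start date". Section 12.0 widens this: "all patients who come off study will be followed for survival every 4 months for up to 2 years from study start date". Table 10.1 footnote 20 says that all treated patients are "followed for survival every 4 months with phone calls for up to 3 years from study start date". For patients who stop for toxicity, the synopsis (study assessments) says "they will be followed for progression and for survival at least every 4 months up to 3 years".

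**Progression after stopping for toxicity.** Footnote 14 of Table 10.1 says "subsequent restaging scans will be requested and assessed at least every 4 months for up to 2 years from study start date", and Section 11.5 says "subsequent imaging, if available, will be requested every 4 months up to 2 years from study start date to document time of progression". Footnote 20 of the same table follows these patients with visits or "by request of outside medical records every 4 months up to 3 years from study start date", and the synopsis sentence above also gives 3 years.

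**The clock.** Apart from the synopsis, which names no starting point, every limit runs from the 'study start date'. Neither the body nor Appendix 1 defines it. OS itself starts at registration in Section 4.2 and at first treatment in Section 13.1.4; Section 6.3 keeps these within 5 working days of each other.

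**Use of the data.** Section 17.2 plans a Kaplan-Meier median OS with a Brookmeyer-Crowley interval. It states neither a confidence level nor a transformation. The synopsis and Section 17.1 anticipate 24 months of accrual and 12 of follow-up. Section 7.3 adds: "Patients may be treated up to a maximum of two years from the time of treatment initiation".

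**The concern.** The populations overlap, so both texts cannot be followed. A treated patient who comes off study falls under Section 12.0 (2 years) and footnote 20 (3 years) at once, and the study team cannot tell when contact should stop.

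The undefined clock makes the 2-year text awkward on either reading:

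- **Per patient.** Someone who completes the two years of treatment allowed by Section 7.3 has no survival follow-up left beyond the vital-status check at the 30-day discontinuation visit.
- **From trial opening.** Follow-up stops at month 24, just as accrual is due to end, so the last patients enrolled contribute almost nothing to OS.

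What is at stake is how much OS data the trial collects, and so how well it can estimate a median it has planned to report.

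**Working it through.** **Figures the plan gives.** It states no precision figure for OS. Its response-rate design (stop at 2 or fewer of 13, reject at 9 or more of 29) reproduces: exact type I error 0.0999 and power 0.804, against the stated 0.10 and 80%. Neither depends on survival follow-up.

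**Inputs from the documents.** 29 patients (Section 17.1); 24 + 12 = 36 months to the planned end; median OS about 18 months (Section 1.1, a background figure and not a planning assumption).

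**Assumptions added.** Exponential survival, uniform accrual, no dropout, all 29 patients accrued, 95% level. Each patient's OS is censored at the earlier of the data cut and 24 or 36 months from entry.

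**Complete follow-up (exact).** With d deaths, S = 1 − d/29 and se = √(S(1−S)/29). The upper limit for the median exists once S + 1.96·se ≤ 0.5.

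- d = 19: 0.345 + 1.96 × 0.088 = 0.518, so no limit.
- d = 20: 0.310 + 1.96 × 0.086 = 0.479, so a limit exists. Twenty deaths are needed.
- At median 18, the chance of death is 1 − 2^(−24/18) = 0.603 by 24 months and 1 − 2^(−36/18) = 0.750 by 36 months.
- P(19 or fewer deaths of 29) is 0.775 under the 2-year limit and 0.166 under the 3-year limit.

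**Month-36 cut (simulation, Kaplan-Meier with Greenwood variance).** The upper limit is the first time the upper pointwise band is at or below 0.5. With follow-up to 36 months the curve can fall to zero on a few late patients, where the variance is undefined. Results therefore depend on whether such a curve counts as giving a limit.

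| Median 18 months | 2-year limit | 3-year limit |
|---|---|---|
| Median reached | 84% | 96% |
| Mean deaths | 15.9 | 17.1 |
| Upper limit missing, linear, zero counted | 81% | 50% |
| Upper limit missing, linear, zero not counted | 81% | 55% |
| Upper limit missing, log, zero counted | 95% | 83% |
| Upper limit missing, log, zero not counted | 95% | 91% |

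**Sensitivity to the assumed median (linear, zero counted).** The missing share is 25% vs 8% at 12 months, 55% vs 25% at 14.7 months (the sorafenib arm cited in Section 1.2.4) and 97% vs 80% at 24 months. At 24 months the median itself is reached in 50% vs 81%.

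**If the clock is trial opening (data end at month 24 or 36; median 18, linear, zero counted).** The upper limit is missing in 88% vs about 50%, and the median is reached in 65% vs 96%.

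**Contacts, median 18, every 4 months.** S(t) = 2^(−t/18).

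- *Per-patient clock, against the 2-year text.* Three further checks for everyone alive at 24 months: 29 × 0.397 × 3 = 34.5. If contact stops once a death is known: 29 × (0.397 + 0.340 + 0.292) = 29.8. Ceiling 29 × 3 = 87.
- *Trial-opening clock, against footnote 20.* A patient entering at month e has follow-up to 36 − e and would gain the contacts from there to month 36. Averaged over e, counting contacts made while alive: 29 × (0.250 + 20/24 × 0.292 + 16/24 × 0.340 + 12/24 × 0.397 + 8/24 × 0.463 + 4/24 × 0.540) ≈ 34. If all survive: 29 × 3.5 ≈ 102.
- *Trial-opening clock, against the 2-year text.* The same sum starting from 24 − e gives about 79; if all survive, 29 × 6.5 ≈ 189.

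**The case against.** The strongest reply is that little rests on this. No OS hypothesis or decision uses the upper limit. An open limit can be reported, and Section 1.2.5 cites one for another trial. The plan has no OS assumption and no OS data cut-off, so any percentage is conditional. All of that stands, and it is why the figures are an illustration and the contradiction is the finding.

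The choice of limit can also be contested. Accrual of 24 months plus follow-up of 12 is 36 months, exactly 3 years from trial opening, so footnote 20 may have meant that. Counting 3 years from each registration would then extend follow-up for all but the earliest patients. This stands too: the documents require only that the texts agree, and the cost depends on the clock.

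A reader might infer more than the documents support:

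- *That the trial's main result is affected.* It is not; the response-rate rule uses no survival data.
- *That 3 years would secure the interval.* It would not; at month 36 and median 18 the upper limit is still missing in about half of trials or more.
- *That the log-interval gain is a firm 95% to 83%.* Most of it depends on counting a curve that falls to zero as giving a limit; otherwise it is 95% to 91%.
- *That PFS is damaged to a known degree.* The conflict over progression follow-up bears on PFS, but its effect has not been quantified.

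**Conclusion.** Wrong as written. The protocol gives two incompatible lengths for survival follow-up, two for progression follow-up after toxicity (with Table 10.1 contradicting itself), and an undefined start for nearly all of them. This holds without any modelling assumption.

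The consequence is lost precision in a secondary estimate. In every scenario run, the 2-year text does worse than the 3-year text. At median 18 and a month-36 cut the linear contrast is 81% vs 50–55%, and it widens to 78% vs 17% once every patient has been followed to the limit. The size depends on the assumed median, the transformation, the data cut and the clock. On the per-patient reading, landmark survival before 24 months is unaffected. The correction should be made, because follow-up that was not collected may be hard to recover later.

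**What to change.** 1. Reconcile the synopsis (study assessments), Table 10.1 footnotes 14 and 20, and Sections 11.5 and 12.0 to one limit for survival, and for progression in patients who stop treatment without progressive disease. The 3 years already in footnote 20 is the natural choice.
2. Replace 'study start date' with each patient's date of registration, the OS origin in Section 4.2, and align the OS definition in Section 13.1.4 with it.
3. In the synopsis study-duration row and Sections 2.0 and 17.1, say that survival contact may continue past month 36, to about month 60 for the last patient (24 + 36), while ORR and PFS are reported on the planned timeline.

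**Cost.** Wording in about nine places. On the per-patient reading there is no extra contact against footnote 20, and about 30 to 35 expected phone or record checks (ceiling 87) against the 2-year text. If 'study start date' meant trial opening, expect about 34 extra contacts against footnote 20 (ceiling about 102) and about 79 against the 2-year text (ceiling about 189). The sponsor should state which reading was intended before accepting the cost.
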